- To assess progression-free survival at 12 months after ASCT in patients at high risk for post-transplant recurrence including patients with persistent and recurrent high risk diffuse large B cell lymphoma, high risk and recurrent T cell lymphoma and high risk and recurrent multiple myeloma.
- To assess blood immune reconstitution, phenotype and TCR repertoire at screening (at time of informed consent), at apheresis (stem cell collection), and then serially the day 1 of week 1 of combined checkpoint inhibitors and then weeks 4, 7, 12, 18 and 26, and at 9, 12, 15, and 18 months post-transplant and at time of relapse, as it occurs. Immune phenotype and TCR will be evaluated as follows:

T cell repertoire analysis

TCR Immunoseg for Vbeta CDR3 highest frequency specificities.

Real-Time PCR analysis:

T-bet(Th1); STAT3, RORgamma t (TH17); STAT6 (Th2); FoxP3 (Treg), granzyme A (GZMA) and perforin (PRF1)

Flow Cytometric Phenotype Analysis for:

T Cells:

CD3; CD4; CD8; CD4+CD25+PD1+; CTLA-4 Follicular Helper T: CD3+,CD4+,CXCR5+,PD1+ CD4 and CD8 T naïve (RO-; CCR7+) Central Memory: (TCM;RO+,CCR7+) Effector Memory (TEM, RO+,CCR7-)

Terminally differentiated effector memory (TEMRA; RO-, CCR7-)

T regulatory cells (Treg): CD4+,CD25hi, CD127low, CD39+, CD152hi, RO-(resting); CD4+,CD25hi, CD127low, CD39+, CD152hi, RO+ (activated)

Dendritic Cells:

Lin-, CD11c+, CD1a+, CD80 (B7-1)low, CD86 (B7-2)low, MHC Class Illow (DC resting); CD11c+, CD1a+, CD123-, CD80hi, CD86hi, HLADRhi (DC1 activated); HLADRhi, CD11c-, CD123+, PDL-1+ (DC2)

Macrophages:

HLADR+, CD14+, CD64+, CD25+, CCR7+ (M1); HLADR+, CD14+, CD64-, CD206+, CD25-, CCR7-, CD209+, PDL-1+ (M2)

Myeloid derived suppressor cells:

HLADR-/low, CD11b+, CD14+,CD33+hi,CD34+, CD66b-, PDL-1+ (M-MDSC); HLADR-, CD11b+, CD14-,CD33+low,CD34+, CD66b+, PDL-1+ (G-MDSC)

B Cells:

CD19+, B7-1low, B7-2low, MHC Class Illow (resting); CD19+, B7-1hi, B7-2hi, MHC Class Ilhi (activated)

Amendment9 09NOV2021 Page 35 of 77

NK cells:

CD16+, CD3-, CD56+

NKT Cells:

CD16+, CD3+, CD56+

Plasma Cytokine levels: Multiplex 25 Cytokine - Luminex

GM-CSF, IL-1b, IL-1RA, IL-2, IL-2R, IL-4, IL-5, IL-6, IL-7, IL-8, IL-10, IL-12, IL-13, IL-15, IL-17, TNF alpha; MCP-1, MIP1a, MIP1b, MIG, RANTES, IFN-alpha, IFN-gamma, IP-10, Eotaxin

- To determine the toxicities resulting from administration of the treatments.

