- To assess tumor site immune phenotype, T cell repertoire and PD L1/2 expression when tissue available for biopsy prior to autologous transplant conditioning and then at time of progression (within 18 months) after autologous transplant conditioning.

The tertiary objectives are:

• To identify specific intestinal microbial strains associated with improved outcome in autologous stem cell transplantation patients treated with combined checkpoint inhibitors. The overall microbial composition in stool samples of patients will be analyzed at screening, preconditioning (to be collected within 48 hours prior to transplant admission), at engraftment (within 72 hours of ANC ≥ 500), and then serially, on day 1 of week 1 (to be collected within 48 hours prior to clinic visit) and then weeks 4, 7, 12, 18, and 26, End of Treatment, and 9, 12, 15 and 18 months post-transplant, and at time of relapse, as it occurs. A 16S ribosomal RNA (rRNA) miSeq Illumina platform will be used for overall microbial composition and quantitative real-time PCR analysis will validate the specific microbial strains identified by miSeq.

Phase IIA

Primary Objective

• To assess progression-free survival at 18 months after ASCT in patients in cohorts that were deemed safe in Phase Ib (no more than 3 treatment-related toxicity) and at least 4 of 7 patients progression free at 18 months in the Phase Ib.

Secondary Objectives

- To assess complete response rate at 3, 6 and 12 months after ASCT in patients at high risk for post-transplant recurrence including patients in the successor expansion cohorts following the Phase Ib trial.
- To assess progression-free survival at 12 months after ASCT in patients at high risk for post-transplant recurrence including patients with in the successor expansion cohorts following the Phase Ib trial.
- Determine the toxicities resulting from administration of the treatments in patients enrolled in the successor expansion cohorts following the Phase Ib trial.
- To assess blood immune reconstitution, phenotype and TCR repertoire at screening (at time of informed consent), at apheresis (stem cell collection), and then serially the day 1 of week 1 of combined checkpoint inhibitors and then weeks 4, 7, 12, 18 and 26, and at 9, 12, 15, and 18 months post-transplant and at time of relapse, as it occurs.

Tertiary Objectives

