8.3.4 Longitudinal analysis of TCR repertoire and blood immune phenotype

Longitudinal analysis of TCR repertoire analysis results reported as diversity scores will be conducted on samples as determined by DNA sequencing and analyzed by ImmunoSeq software (Adaptive Biotechnologies). TCR repertoire diversity scores in evaluable patient samples will be over time using mixed model repeated measures (MMRM) by utilizing PROC MIXED SAS 9.4. In this models, the status of infection as a time-dependent will be included to examine the effect of both time and infection on cell cytokine levels.

Longitudinal analysis will be performed on blood samples collected at 14 time points:

- 1) Screening Visit (at time of informed consent)
- 2) Apheresis Sample (except for group F, due to stem cell collection having occurred previously). For those patients who sign informed consent after apheresis has already occurred, the Apheresis Sample will be performed on the previously collected, frozen product.
- 3) Day 1 of Week 1 of combined checkpoint therapy,
- 4) Day 1 of Week 4 of combined checkpoint therapy,
- 5) Day 1 of Week 7 of combined checkpoint therapy,
- 6) Day 1 of Week 12 of combined checkpoint therapy,
- 7) Day 1 of Week 18 of combined checkpoint therapy, and
- 8) Day 1 of Week 26 of combined checkpoint therapy.
- 9) End of Treatment Visit
- 10) Post-transplant, 9 months,
- 11) Post-transplant, 12 months,
- 12) Post-transplant, 15 months.
- 13) Post-transplant, 18 months and / or
- 14) Relapse, as it occurs.

Cell counts in all subsets will be analyzed as repeated measurements obtained at the 14 timepoints to examine the changes over time or less when time of relapse as the last timepoint. This longitudinal analysis will be performed by fitting an overall model across subsets of cells and a separate longitudinal analysis within each subpopulation.

1. Overall model

Using all subsets, T cells, (T cells (CD4 versus CD8, Tregs, memory (central versus effector versus terminally differentiated effector memory), dendritic cells, macrophages, myeloid suppression cells, B cells, NK cells, NKT cells, analysis of cell counts will be performed to examine changes in counts over time (14 time points) and difference in counts between levels

Amendment9 09NOV2021 Page 39 of 77

of their state, naïve versus activated, as appropriate. The covariates in this model will be timepoints (14 timepoints listed above) and subset of cell population.

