- 2. Within each subset, the following separate longitudinal analysis of cell counts over time will conducted:
 - i. Count of dendritic cells as a function of time (14 timepoints) and status (DC1 versus DC2).
 - ii. Count of DC2 as a function of time (14 timepoints) and PDL-1+/- status,
 - iii. Count of macrophages as a function of time (14 timepoints) and status (M1 versus M2)
 - iv. Count of M2 cell as a function of time (14 timepoints) and PDL-1+/- status,
 - v. Count of CD4 T cells as a function of time (14 timepoints) and follicular helper function status.
 - vi. Count of T cells as a function of time (14 timepoints) and activated status (activated versus naïve),
- vii. Count of activated T cells as a function of time (14 timepoints) and PD1+/- status,
- viii. Count of Tregs as a function of time (14 timepoints) and activated status (activated versus resting),
- ix. Count of memory T cells as a function of time (over 14 timepoints) and type of memory cells (effector versus central memory versus terminally differentiated effector memory,
- x. Count of B cells as a function of time (14 timepoints) and activated status (activated versus resting),
- xi. Count of myeloid suppressor cells as a function of time (14 timepoints) and PDL-1+/-status,

For these count variables, Poisson Regression Analysis based on generalized estimating equations (GEE) method will be performed by utilizing the procedure PROC GENMOD SAS 9.4 with Poisson distribution, log link function and independent covariance structure.

Continuous variables such as cytokine levels (GM-CSF, IL-1b, IL-1RA, IL-2, IL-2R, IL-4, IL-5, IL-6, IL-7, IL-8, IL-10, IL-12, IL-13, IL-15, IL-17, TNF alpha; MCP-1, MIP1a, MIP1b, MIG, RANTES, IFN-alpha, IFN-gamma, IP-10, Eotaxin) will be examined over time (14 timepoints) using mixed model repeated measures (MMRM) by utilizing PROC MIXED SAS 9.4. In both of the models to be fit to these immune markers, the status of infection as a time-dependent covariate will be included to examine the effect of both time and infection on cell cytokine levels.

8.3.5 Longitudinal analysis of the gut microbiome.

The time points of stool sample collection are:

- 1) Screening Visit (up to 7 days post consent). If patient signs consent within 7 days of transplant admission, stool sample collection will start from item "2" (Preconditioning)
- 2) Preconditioning (to be collected within 48 hours prior to transplant admission)
- 3) Engraftment, (within 72 hours of ANC > 500)

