- 4) Day 1 of Week 1 of combined checkpoint therapy.
- 5) Day 1 of Week 4 of combined checkpoint therapy,
- 6) Day 1 of Week 7 of combined checkpoint therapy,
- 7) Day 1 of Week 12 of combined checkpoint therapy.
- 8) Day 1 of Week 18 of combined checkpoint therapy, and
- 9) Day 1 of Week 26 of combined checkpoint therapy.
- 10) End of Treatment Visit
- 11) Post-transplant, 9 months,
- 12) Post-transplant, 12 months,

Amendment9 09NOV2021 Page 40 of 77

- 13) Post-transplant, 15 months.
- 14) Post-transplant, 18 months and / or
- 15) Relapse, as it occurs.

Counts of specific intestinal microbial strains will be examined overtime (15 time points) using Poisson regression analysis utilizing PROC GENMOD as described in analysis of blood immune markers. In each of the models for each microbial strain, status of infection as a time-dependent covariate will be included as microbial along timepoint variable.

The overall microbial composition will be determined by 16S rRNA miSeq Illumina platform and analyzed by Second Genome Solutions proprietary 16S bioinformatic data analysis software package.

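### The correlative models have no primary contrast, false-discovery rule or exploratory label, and no scale is stated for the cytokines

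*Combined protocol and SAP*

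**What the plan says.** Section 8.3.4 describes the blood analyses as "fitting an overall model across subsets of cells and a separate longitudinal analysis within each subpopulation". The within-subset list runs from i to xi, so there are 11 subset models, fitted by Poisson GEE with a log link. TCR diversity has its own mixed model. The cytokine panel is given in Section 8.0 as "Plasma Cytokine levels: Multiplex 25 Cytokine - Luminex"; the list in Section 8.3.4 also counts to 25, and these levels "will be examined over time (14 timepoints) using mixed model repeated measures (MMRM) by utilizing PROC MIXED SAS 9.4". Infection status enters as a time-dependent covariate.

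For stool, Section 8.3.5 says: "Counts of specific intestinal microbial strains will be examined overtime (15 time points) using Poisson regression analysis utilizing PROC GENMOD". Infection status is added "In each of the models for each microbial strain". There is no list, cap or filter for strains. The tertiary objective in Section 8.0 is "To identify specific intestinal microbial strains associated with improved outcome in autologous stem cell transplantation patients".

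For these models the document gives no significance level, primary contrast, test family, false-discovery or family-wise procedure, or exploratory label. Its stated significance levels belong to the 18-month PFS test (Section 8.1) and the toxicity boundary (Section 8.6). No analysis scale is written for cytokines. Section 8.4.3 mentions normality only for choosing descriptive summaries. Sections 8.3.4 and 8.3.5 do not say whether the models are fitted by cohort or on pooled patients, whereas Sections 8.3.1 to 8.3.3 refer to each cohort.

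**The concern.** The product of these analyses is a list of markers that changed and, for stool, of strains said to be identified. A plan that sets out to identify something needs a rule for what counts. Here, one marker could be tested once jointly over time, at each visit against baseline, or for infection as well as time, and nothing fixes the choice before the data are seen. A reader of the results could not tell how many tests lay behind a reported p-value.

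The cytokine scale is a separate gap. Concentrations are positive and often right-skewed, and their changes are usually described as fold-changes. The plan gives the counts a log link but nothing comparable for cytokines. Followed literally, PROC MIXED would model the values as recorded, which can waste information in small groups. At stake is how the marker findings may be described.

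**Working it through.** The plan states no error rate or power for these analyses, so there is no figure to reproduce.

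**Inputs from the document.** 25 cytokines, 11 subset models, 14 blood and 15 stool time points (Sections 8.3.4 and 8.3.5); 7 patients per Phase Ib cohort, 42 in all, and 37 per expansion cohort (Section 8.1).

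**Assumed.** Two-sided 0.05 (0.10 as a range), independent tests, 100 to 200 strains, a two-fold change, log-SD 0.5 to 1.5, within-patient correlation 0.5.

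**False positives if nothing changes.** Expected number = m × α; chance of at least one = 1 − (1 − α)^m.
- Cytokines and subsets, one test each: m = 25 + 11 = 36. 36 × 0.05 = 1.8; 1 − 0.95^36 = 0.84. At 0.10: 3.6 and 0.98.
- With the overall and TCR models: m = 38, giving 1.9 and 0.86.
- Testing infection as well as time in the 36 models: m = 72, giving 3.6 and 0.975.
- 36 plus 100 strains: 136 × 0.05 = 6.8. 36 plus 200 strains: 236 × 0.05 = 11.8.
- 13 visit contrasts in each of the 36 models, if done: 468 × 0.05 = 23.4.

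**Share of findings that are false.** With a fraction π of markers truly changing, the share is (1 − π)α / [(1 − π)α + π × power]. For 36 tests:
- π = 0.5, power 0.8: 0.9 / (0.9 + 14.4) = 6%.
- π = 0.1, power 0.3: 1.62 / (1.62 + 1.08) = 60%.

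**Scale.** Take one paired contrast on a log-normal marker. On the log scale the SD of the difference is σ√(2(1 − 0.5)) = σ, so the noncentrality of the t-test is ln 2 × √n / σ. This is 1.83 at n=7, σ=1.0; 4.22 at n=37, σ=1.0; and 2.81 at n=37, σ=1.5. Raw-scale power was simulated.

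| n | log-SD | raw power | log power |
|---|---|---|---|
| 7 | 0.5 | 0.76 | 0.86 |
| 7 | 1.0 | 0.16–0.17 | 0.34 |
| 7 | 1.5 | 0.05 | 0.18 |
| 28 | 0.5 | 1.00 | 1.00 |
| 37 | 0.5 | 1.00 | 1.00 |
| 37 | 1.0 | 0.84–0.85 | 0.98 |
| 37 | 1.5 | 0.34 | 0.78 |
| 42 | 1.0 | 0.88 | 0.99 |

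With no true change, the raw-scale test rejected in roughly 1.5% to 5% of runs, so it was not anti-conservative in this setting.

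**Effect of Benjamini-Hochberg at q ≤ 0.10.** Simulation on the log scale with 36 tests as one family, 11 truly changing two-fold, log-SD 1.0:
- n=7: false findings 1.24 to 0.17; true findings 3.7 to 0.89; per-marker power 0.34 to 0.08.
- n=37: false findings 1.23 to 0.85; true findings 10.82 to 10.71; per-marker power 0.98 to 0.97.

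**The case against.** The strongest reply is that these are secondary and tertiary analyses in a trial whose Phase Ib part is declared an unpowered pilot. Expansion and stopping rest on 18-month PFS and toxicity (Sections 8.1 and 8.6). The blood models are enumerated; only the strain list is open. One joint time test per model is as consistent with the text as 13 contrasts. A global null is also a weak benchmark for a series running from before conditioning to 18 months after transplant, when immune reconstitution is expected. All of this stands and limits the size of the point.

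It does not remove it. The plan never calls these analyses exploratory, and the blood analyses serve a secondary objective. The planned quantitative PCR re-measures strains found by sequencing; it is not a multiplicity procedure, and no independent patient sample is described.

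A reader might infer several stronger things that the documents do not support:
- That the plan analyses cytokines on the raw scale. It is silent on scale; raw is only the literal default.
- That a raw scale would inflate false positives. In the check above it did not.
- That most reported blood markers will be chance. About two false positives are expected from 36 single tests, and the false share depends on quantities the plan does not give.
- That missing false-discovery control causes real markers to be missed. Missed markers follow from scale and sample size, and false-discovery control lowers power further.
- That every model has only 7 to 37 patients. Pooled fitting is not excluded.

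**Conclusion.** The gap is real and modest. No primary contrast, error-rate rule, exploratory label or cytokine scale is specified for at least 38 blood models and an unstated number of strain models. The false-positive burden is about 1.8 for the 36 cytokine and subset models at one test each, about 7 to 12 with 100 to 200 strains, and higher with per-visit contrasts. These figures assume a 0.05 level, independence and no true change.

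The possible loss from leaving cytokines untransformed depends on skewness and sample size. It is material at log-SD 1.0 or more at the cohort sizes of 7 and 37, and negligible at log-SD 0.5 with 28 or more patients. It bears on power, not on false positives.

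For strains, a multiplicity rule alone would not suffice. The planned models contain time and infection but no outcome term, so even a well-controlled time effect cannot show association with improved outcome. No expansion or efficacy decision is affected; the consequence is for what may be claimed about markers.

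**What to change.** Before the correlative data are analysed, amend Sections 8.3.4 and 8.3.5 to:
1. Model cytokines as log2 concentration, with a stated rule for values below the detection limit, and report fold-changes.
2. Name one test of change per marker, for example a joint test over the scheduled times, and say whether models are fitted by cohort or pooled.
3. Within each family (cytokines, cell subsets, strains), report Benjamini-Hochberg q-values beside the unadjusted p-values. Use *identified* only for markers that meet a prespecified q threshold, such as 0.10, and label the rest exploratory.
4. For strains, state how candidates are selected for testing, and apply the q threshold to a test of association with outcome rather than to change over time.

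The cost is plan wording, an outcome model for strains and one added adjustment step. The downside is a shorter list of identified markers: a large loss at n=7 and a small one at n=37. Showing both q-values and unadjusted p-values keeps the weaker signals visible for later work.

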8.4.2 Evaluation of tumor site phenotype

Absolute number of PD-L1/L2-bearing activated helper T cell subpopulations from biopsy at tumor site will be examined for two time points prior to conditioning and time of progression (within 18 months post-transplant) using Poisson regression analysis with GEE described in analysis of blood phenotype above.

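### The Poisson models for stool strain counts (8.3.5) and biopsy cell numbers (8.4.2) have no offset, so any difference in the amount sampled passes into the reported time ratio

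*Combined protocol and SAP*

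**What the plan says.** The analysis of strains in section 8.3.5 reads: "Counts of specific intestinal microbial strains will be examined overtime (15 time points) using Poisson regression analysis utilizing PROC GENMOD". The details are taken over from the blood immune markers in section 8.3.4, where the model is specified "with Poisson distribution, log link function and independent covariance structure".

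The listed terms are few. For the strain models, 8.3.5 names the time point and adds that "status of infection as a time-dependent covariate will be included". For the overall blood model, 8.3.4 says: "The covariates in this model will be timepoints (14 timepoints listed above) and subset of cell population".

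Section 8.4.2 takes as its outcome "Absolute number of PD-L1/L2-bearing activated helper T cell subpopulations from biopsy at tumor site", compared between two time points (before conditioning and at progression) with the same Poisson GEE.

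On the laboratory side, 8.3.5 says: "The overall microbial composition will be determined by 16S rRNA miSeq Illumina platform", with the output "analyzed by Second Genome Solutions proprietary 16S bioinformatic data analysis software package". The tertiary objectives (sections 1.0 and 8.0) give quantitative PCR the role of validating the strains that sequencing identifies. Nowhere do the documents mention an offset, exposure term, read total, rarefaction, relative abundance, total cells counted, or tissue area or weight.

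**The concern.** A count from a sample is the product of two things: how much material was examined and how abundant the target is in it. The plan wants to learn about the second. A log-link model without a term for the first estimates the product, so its time effect can come from abundance, from the amount examined, or from both. The robust standard errors of GEE deal with the variance and do not correct a wrong mean model. Infection status does not stand in for the amount sampled.

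For biopsies, the protocol itself leaves room for such a difference. Section 6.1 accepts new or archival tumor tissue, or bone marrow, at screening. Section 6.2.3 calls for a lymph node and/or bone marrow biopsy at progression. No standard amount is set for either, so the two samples compared in 8.4.2 can differ in tissue type and in quantity.

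At stake is the reading of the tumor-site phenotype (a secondary objective) and of strain changes over time, which feed the tertiary aim of finding strains linked to better outcome.

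**Working it through.** The plan gives no sample size, power or expected effect for these models, so there is no figure of its own to reproduce.

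**Step 1: algebra.** Let A be the amount sampled (reads, tissue area or cells counted) and p the abundance per unit. Then E(count) = A × p, and with a log link:

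log E(count) = log A + log p

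If log A is omitted, the time coefficient estimates log(A2/A1) + log(p2/p1), so

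estimated time ratio = (A2/A1) × (p2/p1)

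With log A as an offset, only p2/p1 remains.

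**Step 2: numbers.** Assumed inputs, none from the documents: 20,000 reads at the first time point and a strain at 1%.

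- First time point: 20,000 × 0.01 = 200 expected reads.
- Twice the depth, same abundance: 40,000 × 0.01 = 400. Ratio without offset: 400/200 = 2.0. With offset: (400/40,000)/(200/20,000) = 1.0.
- Depth ratio 1.5: 300/200 = 1.5. Depth ratio 4: 800/200 = 4.0.
- The error can also hide a change: a true halving at twice the depth gives 0.5 × 2 = 1.0.

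The same arithmetic holds for a biopsy with twice the tissue area at equal cell density.

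**Step 3: simulation of the documented model.** Poisson GEE, log link, independence, robust errors, two time points, constant true abundance. Cohort sizes of 7 (Phase Ib) and 37 (Phase IIA) come from section 8.1. All else is assumed: the Step 2 inputs, between-patient log-SD 0.5, within-time depth CV 30%, 500 runs per setting.

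| n | Depth ratio | Median ratio, no offset | p<0.05, no offset | Median ratio, offset | p<0.05, offset |
|---|---|---|---|---|---|
| 7 | 0.5 | 0.506 | 96.2% | 1.002 | 16.4% |
| 7 | 0.75 | 0.745 | 54.4% | 1.001 | 16.6% |
| 7 | 1 | 0.994 | 13.6% | 0.995 | 14.6% |
| 7 | 1.5 | 1.497 | 74.6% | 0.998 | 16.8% |
| 7 | 2 | 1.987 | 97.8% | 1.006 | 13.6% |
| 37 | 0.5 | 0.499 | 100% | 1.001 | 6.6% |
| 37 | 0.75 | 0.752 | 93.2% | 1.001 | 5.2% |
| 37 | 1 | 1.001 | 6.2% | 1.001 | 7.8% |
| 37 | 1.5 | 1.496 | 99.8% | 0.998 | 7.0% |
| 37 | 2 | 1.983 | 100% | 0.999 | 6.6% |

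The depth ratio passes into the time ratio one-for-one, and the offset removes it. The excess over 5% at n=7 with the offset reflects robust errors in small samples and is a separate matter.

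**Step 4: random differences only.** At depth ratio 1 there is no bias, as the table shows, but precision is lost. Under the same assumptions, one count of 200 has Poisson variance of about 1/200 = 0.005 on the log scale; a depth CV of 30% adds ln(1 + 0.3²) = 0.086. The SD of one patient's log ratio between two samples then rises from √(2 × 0.005) = 0.10 to √(2 × 0.091) = 0.43.

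**The case against.** The strongest reply concerns stool. The plan never says that the modelled strain counts are sequencing reads. It assigns 16S sequencing to overall composition and mentions specific strains together with quantitative PCR. If the counts are PCR quantities, read depth is irrelevant. The proprietary software might also normalise reads before modelling. Both stand as possibilities, but neither is written down. In either case the outcome would no longer be a raw count, and 8.3.5 would have to say what it is and per what unit.

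A second reply is that nothing shows the amount sampled to differ systematically by visit. A reader might infer that read depth is known to shift between screening, engraftment and follow-up. The documents do not support that, and the 2-fold figure is only an illustration. What stands is conditional: if amounts differ systematically the time ratio is biased, and if they vary at random it is noisier.

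A reader might also extend the point to the T-cell receptor analysis, where "TCR repertoire diversity scores in evaluable patient samples will be over time using mixed model repeated measures". That does not follow. The outcome there is a continuous score in a mixed model, so the log-link algebra does not apply. How the ImmunoSeq software handles sample size is not described. Adjusting for template number could also remove part of the immune recovery that the study wants to measure.

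Finally, these are secondary and tertiary analyses with no stated error rate or decision rule. That is correct and limits the weight of the point.

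**Conclusion.** The point holds in a bounded form. As written, 8.3.5 and 8.4.2 specify a Poisson GEE with log link and no offset, so a k-fold difference in the amount sampled multiplies the reported time ratio by k, while random differences cost precision. An assumed 2-fold difference would appear as 2.0 (1.5 to 4.0 over the assumed range) with no biological change.

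It is firmest for 8.4.2, where the outcome is explicitly an absolute number and the protocol allows different tissue at the two time points. For 8.3.5 it holds if the modelled counts are unnormalised reads; otherwise the defect is that the source and unit of the outcome are not stated. The size of any actual bias cannot be derived from the documents. The expansion criteria, the test of 18-month PFS and the toxicity stopping rules are unaffected. The change should be made before these data are analysed, because a denominator chosen afterwards could be chosen by its result.

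**What to change.** - **Section 8.4.2:** add an offset of log(total cells counted) or log(tissue area evaluated), naming which one. Compare like tissue types, since an offset corrects for amount and not for the difference between, say, lymph node and marrow.
- **Section 8.3.5:** state the source of the strain counts. If they are 16S reads, add an offset of log(total quality-filtered reads in the sample). If they are qPCR quantities, replace the Poisson model with an analysis of log copies per gram of stool or per total 16S copies.

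The SAS change is small: one derived variable and the OFFSET option in PROC GENMOD. The real cost lies with the laboratory, which must record and export the denominator for every sample; the documents do not describe doing so, and for archival tissue it may need a short specification. With the read offset, stool results become relative rather than absolute abundance, so a rise in one strain lowers the shares of others. The report should say so.
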